6.4.6 Overdose of Trial Medication

There are no special recommendations for overdose of N-3 PUFA. Treatment should be symptomatic.

6.4.7 Protocol Treatment Discontinuation

In consenting to the trial, participants are consenting to trial treatment, trial follow-up and data collection. However, an individual participant may stop treatment early or be stopped early for any of the following reasons:

- Unacceptable treatment toxicity or adverse event.
- Inter-current illness that prevents further treatment.
- Any change in the participant's condition that in the clinician's opinion justifies the discontinuation of treatment.
- If a participant becomes pregnant, they will be advised to stop trial treatment immediately (and if 12 week dispensing was scheduled this will not take place). The participant can and should be encouraged to remain in the trial for follow up measures as far as possible.
- Withdrawal of consent for treatment by the participant.
- Where patients are unable or unwilling to continue to undertake study measurements/activities, the decision as to whether the participant should continue with trial treatment and/or follow-up assessments will be at the discretion of the local PI and/or CI.

As participation in the trial is entirely voluntary, the participant may choose to discontinue trial treatment at any time without penalty or loss of benefits to which they would otherwise be entitled. Although not obliged to give a reason for discontinuing their trial treatment, a reasonable effort should be made to establish this reason, whilst remaining fully respectful of the participant's rights.

Participants who discontinue protocol treatment, for any of the above reasons, should remain in the trial for the purpose of follow up and data analysis.

6.5 Outcomes

6.5.1 Primary Outcome

The primary outcome will be asthma control as assessed by change in asthma control questionnaire (ACQ)-6 mean score (http://www.qoltech.co.uk/index.htm) at 24 weeks post-randomisation of n-3 PUFA versus placebo. The ACQ-6 has six questions: five questions about symptoms and one about reliever inhaler usage. The five symptom questions are 1) woken at night by symptoms, 2) wake in the mornings with symptoms 3) limitation of daily activities 4) shortness of breath and 5) wheeze. Patients are asked to recall how their asthma has been during the previous week and to respond using a 7-point scale (0 = no impairment, 6 = maximum impairment).

6.5.2 Secondary Outcomes

The following secondary outcomes will be assessed comparing n-3 PUFA to placebo:

Asthma control

 Measured using an ACQ-7 which is the same as the ACQ-6 (above) with the addition of FEV1 % predicted (http://www.qoltech.co.uk/index.htm) at baseline 12 and 24 weeks.

General Health Related and Disease Specific Quality of Life:

Participants to complete the following questionnaires at baseline and 12 weeks and 24 weeks postrandomisation to assess outcomes listed:

- Asthma related quality of life assessed by the Mini Asthma Quality of Life Questionnaire (mini-AQLQ) will be measured at baseline, 12 weeks and 24 weeks(26). The minimum clinically important difference in scores is 0.5.
- Health-related quality of life indicated by the EQ5D-5L questionnaire to estimate quality adjusted life years(27).
- Sino-nasal disease related quality of life as assessed by the Sino-Nasal Outcomes Test (SNOT)-22(28).

Lung and Nasal Function:

- Peak nasal inspiratory flow (PNIF) will be captured every six weeks throughout the study at home (29) (where possible).
- Peak expiratory flow will be captured every six weeks throughout the study at home.
- FEV₁ and forced expiratory flow at 50% of vital capacity (FEF₅₀) will be obtained from spirometry, measured post-bronchodilator according to current American Thoracic Society/European Respiratory Society Taskforce guidelines(30). It will be measured at baseline, 12 weeks and 24 weeks (where possible). It will be reported as part of the ACQ-7 and as a separate secondary outcome.

Type 2 airway inflammation

- Fraction of exhaled nitric oxide (FeNO) will be measured, at baseline, three months and six months, using a NIOX MINO nitric oxide analyser (Aerocrine, Chicago, USA), according to the National Institute for Health and Care Excellence guidelines (www.nice.org.uk/guideance/dg12).
- Induced or spontaneous sputum (subgroup) will be collected at baseline and 24 weeks for percentage eosinophil count. Induced sputum will be collected as described by Pizzichini et al (31), sputum will be processed as described by Pizzichini et al(32) for analysis of SPM. Total cell count will be calculated and cell viability determined. Cytospins will be prepared and stained by Wright's stain for differential cell count.
- Full blood count will be measured at baseline, 12 weeks and 24 weeks for assessment of the concentration of eosinophils.

Cyclooxygenase pathway

• A urine sample will be collected at baseline and after 24 weeks of therapy. It will be analysed for LTE4 and PGD2 by radioimmunoassay and corrected for urinary creatinine.

Adherence

 Venous blood will be collected at baseline, 12 weeks and 24 weeks for assessment of red blood cell fatty acid concentration. In the situation that venous blood is not available, red blood cell fatty acid concentration will be obtained from a finger prick blood sample, which will be collected using a dried blood spot sample card and mailed to the Norwich Research Park Biorepository. • Food frequency questionnaire (FFQ) will be completed at baseline and 24 weeks using the validated European Prospective Investigation of Cancer (EPIC) FFQ(33). The FFQ will be analysed using the online McCance and Widdowson's composition of foods integrated dataset, in order to establish habitual dietary intake, and in particular EPA and DHA.

Specialised pro-resolving mediators (SPM)

 Induced or spontaneous sputum (subgroup) will be collected at baseline and 24 weeks for SPM. Sputum samples will be acidified, applied to solid-phase extraction cartridges and the eluted SPM will be analysed by liquid chromatography-tandem mass spectrometry as described by Barden et al (34).

Asthma attacks and safety:

- Asthma attacks will be defined as those resulting in death, hospitalisation, A&E attendance, out-of-hours medical contact, or a course or boost in oral corticosteroids (prednisolone) of at least 3 days for asthma.
- Adverse events will be recorded at each study visit following randomisation.
- Full blood count, renal and liver function tests, and coagulation for those receiving warfarin will be measured in local laboratories at baseline, 12 weeks and 24 weeks.

6.6 Participant Timeline

Figure 2. Schedule of Assessments

	Screening ¹	Baseline ¹	Randomisation	6 weeks	12 Weeks	18 Weeks	24 Weeks
				(+/-1 week)	(+/-2 weeks)	(+/- 2 weeks)	(+/- 4 weeks)
Informed Consent	Х						
Eligibility	Х						
Demographics, medical history and patient characteristics collected		x					
Urine pregnancy testing for WOCBP		x			x		
Randomisation			Х				
IMP dispensed			Х		X		
IMP adherence					X		X
ACQ-6	Х	X		Х	X	х	X
PNIF (where possible)		X		Х	X	Х	X
Peak expiratory flow		X		Х	X	Х	X
Spirometry		X			X		X

AQLQ		Х		Х	Х
EQ-5D-5L		Х		Х	Х
FFQ		Х			Х
SNOT-22		Х		Х	Х
FeNO		Х		Х	Х
Venous blood for ²					
FBC (Eosinophils)					
RBC fatty acid (dried blood spot sample)		х		х	х
Safety – U&E, LFTs Clotting					
Urine sample –for					
LTE4	X (uLTE4 only)	х			х
PGD2					
Sputum – induced or spontaneous ³ for					
Differential cell count		Х			х
SPM					
Asthma attacks			Х		

Adverse events X X X X X						
	Adverse events		Х	Х	Х	х

¹ Patients can be re-screened as required.

²15ml blood to be taken for each safety and biomarker analyses at all study visits.

³ only for those consenting to the sputum sub-study.

NB where study assessments are completed within 28 days of randomisation for baseline or within the timeframes specified above, these observations can be recorded at the relevant time point to avoid patients having to repeat assessments unnecessarily provided they adhere to the requirements of this protocol.

6.6.1 Participant Assessments

6.6.1.1 Visit settings

The study requires venous blood sampling, spirometry, FeNO assessment and, in a subgroup, sputum acquisition and therefore needs to be undertaken in clinical research or other appropriate facilities. Questionnaires will be completed online, or on paper, at home or in another suitable setting and PEF undertaken at home and the results captured electronically, or on paper, at home.

6.6.1.2 Participant Correspondence

Participant correspondence will be via the local research team.

6.6.1.3 Screening

The PI or delegate is responsible for identifying eligible patients to invite to participate in the study in accordance with the eligibility criteria defined in section 6.3.1. Patient's aspirin/NSAID tolerance/N-ERD status will be reviewed and classified as (1) clear history of N-ERD, (2) high probability of diagnosis of N-ERD or (3) clear aspirin/NSAID tolerant. Eligible patients (1) or probably eligible patients (2) will be approached in clinic or identified via local patient lists or clinical records and provided with the relevant study specific literature explaining the aims, methods and potential hazards and benefits of participation in the trial (see section 6.8.1) either in person or by mail.

Patients will be given adequate time to consider their participation prior to the site seeking written informed consent electronically or paper-based following consultation in person or via phone/video call. Informed consent will be sought prior to completion of any assessments/procedures etc. required by the study outside the remit of usual care for patients in the same situation.

The potential participants will be informed prior to consenting that recruitment to the trial is dependent on the results of their screening assessments, including blood tests and a urine and/or nasal aspirin challenge test if required.

6.6.1.4 Baseline

Once written informed consent has been obtained, either in person, electronically or remotely via video/phone, the patient will be required to complete the following baseline assessments at home electronically or sent by post and returned to the site research team: ACQ-6, PEF, AQLQ, SNOT-22 and food frequency questionnaires. Patient demographics, smoking status (including vaping), alcohol intake, co-morbidities and relevant medical history (including asthma attack frequency over the last 12 months) and concomitant medication (including over-the-counter medication) will be captured by questionnaires and from the medical notes where required and recorded in the eCRF.

Most questionnaires can be completed on paper or electronically, however the ACQ-6 and AQLQ can only be completed on paper. During the consent process participants will be offered the option to complete the other questionnaires electronically. Where possible, participants will complete relevant questionnaires electronically via REDCap at each study time point. Electronic questionnaires may be emailed to the participant's personal email address for completion by those opting to provide responses electronically. They may be completed at home or using computing facilities at the site. Participants opting not to receive the questionnaires electronically and for the ACQ-6 and AQLQ, paper copies will be provided. They may complete the questionnaires at the site and hand them to the research staff or complete them at home and return to the NCTU by freepost, courier or pre-paid envelopes. Participants who meet the initial screening criteria will be invited to attend a study visit for assessment of weight and height, FeNO, and spirometry. Blood samples will be taken for safety (full blood count (FBC), urea and electrolytes (U&Es), liver function tests (LFTs), coagulation screen) and research (RBC fatty acid concentration) purposes at the recruiting site prior to enrolment. Participants who are WOCBP will also be required to have a urine pregnancy test conducted specifically for the trial. All participants will be asked to provide a sample of urine which will be analysed for LTE4 and PGD2 (details in section 6.6.2.2). Where the abovementioned assessments and/or data is captured as part of standard care within 28 days of randomisation within the requirements of this protocol, these observations may be recorded as the baseline values to avoid patients having to repeat procedures unnecessarily.

For those meeting the inclusion criteria other than a confirmed diagnosis of N-ERD but a high probability of being aspirin/NSAID intolerant (group 2 shown in figure 3 below) an aspirin challenge will be undertaken at a screening visit and those positive will also be eligible for study recruitment (see section 6.8.1).

Participants consenting to the sputum sub-study at applicable sites will also be required to undergo induced sputum sampling according to previously described protocols(31). A spontaneous sputum sample may be considered an acceptable method of collecting sputum for all patients at a site if COVID-19 restrictions render induced sputum sampling unacceptable. Induced sputum sampling will be undertaken on a separate visit to the aspirin challenge (if required).

6.6.1.5 Randomisation

Upon completion of and when results of all baseline assessments are known, site staff delegated the appropriate responsibility will have the option to randomise the patient. Treatment allocation will be determined by a computer-generated randomisation code via a web-based system facilitated by NCTU. A semi-blinded randomisation outcome will be circulated via email to the site clinical trial pharmacy only. The site PI and delegates will receive a blinded randomisation notification email.

An initial 3-month supply of IMP will be dispensed by the site pharmacy following confirmation of treatment allocation and receipt of a completed trial prescription signed by the PI or delegated subinvestigator. The site pharmacy and research team are responsible for ensuring the participant receives their capsules at an appropriate clinic visit or in exceptional circumstances via courier after liaising with NCTU and receiving approval of the CI.

The participant's General Practitioner (GP) will be informed of their randomisation into the study.

6.6.1.6 Six Week Assessment

The following assessments should be completed at home at 6 weeks post-randomisation: ACQ-6, PEF, adverse event questionnaire and concomitant medication questionnaire. Site staff will contact participants by phone/video call to assess adverse events if they have been flagged on the questionnaire.

Where these assessments are completed as part of standard care and within the time frame permitted by and requirements of this protocol, the results may be recorded for those required at the 6-week study time point.

Participants completing paper-based questionnaires will be provided with a freepost envelope to return them to the trials unit otherwise they will be completed electronically via REDCap.

This assessment may take place +/- 1 week of the scheduled date.

6.6.1.7 12 Week Study Visit

The following assessments should be completed 12 weeks post-randomisation: ACQ-6, PEF, PNIF, AQLQ, SNOT-22, spirometry, FeNO, RBC fatty acids and blood for eosinophils and safety monitoring and urine pregnancy test for WOCBP. Site staff will assess adverse events (including asthma attack frequency) and any changes to concomitant medication and/or medical history.

IMP adherence will be measured by a pill count completed by site staff/participant during the visit. This may be conducted at site where visits take place in person or participants will be asked to confirm the number of remaining capsules via phone/video call. If the participant has reduced their trial treatment dose due to adverse reaction(s) or intolerability this should be documented in the eCRF and a new dosing card administered. Participant should return the superseded dosing card either in person or via freepost envelope.

Participants completing paper-based questionnaires will be provided with a freepost envelope to return them to the trials unit otherwise they will be completed electronically via REDCap.

Where any of these assessments are completed as part of standard care and within the time frame permitted by and requirements of this protocol, the results may be recorded for those required at the 12 week study time point.

Participants will be supplied with a final 12 week supply of IMP (5 bottles whether on full or reduced dose) as prescribed by the PI or delegate, dispensed by the site clinical trial pharmacy. Site staff to ensure patient is administered dosing card with correct treatment schedule. The site pharmacy and research team are responsible for ensuring the participant receives their capsules at this clinic visit.

This visit may take place +/-2 weeks of the scheduled date.

6.6.1.8 18 Week Assessment

The following assessments will be completed 18-weeks post-randomisation: ACQ-6, PEF, adverse event questionnaire and concomitant medication questionnaire. Site staff will contact participants by phone/video call to assess adverse events (including asthma attack frequency) if they have been flagged on the questionnaire.

Where these assessments are completed as part of standard care and within the time frame permitted by and requirements of this protocol, the results may be recorded for those required at the 18-week study time point.

Participants completing paper-based questionnaires will be provided with a freepost envelope to return them to the trials unit otherwise they will be completed electronically via REDCap.

This assessment may take place +/- 2 weeks of the scheduled date.

6.6.1.9 24 Week Visit

The following assessments should be completed 24 weeks post-randomisation: ACQ-6, PEF, PNIF, AQLQ, SNOT-22 and food frequency questionnaires, spirometry, FeNO, urine sample, RBC fatty acids, induced or spontaneous sputum (subgroup) and blood for eosinophils and safety monitoring. Site staff will assess adverse events (including asthma attack frequency) and any changes to concomitant medication and/or medical history.

IMP adherence will be measured by a pill count completed by site staff/participant during the visit. This may be conducted at site where visits take place in person or participants will be asked to confirm the number of remaining capsules via phone/video call. If the participant has reduced their trial treatment dose due to adverse reaction(s) or intolerance this should be documented in the eCRF. Participant should return their dosing card either in person or via freepost envelope.

Participants completing paper-based questionnaires will be provided with a freepost envelope to return them to the trials unit otherwise they will be completed electronically via REDCap.

Participants consenting to the sputum sub-study at applicable sites will also be required to undergo induced sputum sampling according to previously described protocols(31). A spontaneous sputum sample may be considered acceptable method of collecting sputum for all patients at a site if COVID-19 restrictions render induced sputum sampling unacceptable.

Where any of these assessments are completed as part of standard care and within the time frame permitted by and requirements of this protocol, the results may be recorded for those required at the 24-week study time point.

This visit may take place +/- 4 weeks of the scheduled date.

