5.1.1 Explanation for choice of comparators

N-3 PUFA will be compared with matched placebo as this is the most robust way to determine the efficacy and adverse effects of n-3 PUFA. All patients involved in the trial will continue to receive usual care (defined in section 6.4.5).

Treatment allocation is double-blind to reduce potential bias in reporting of the primary outcome and patient reported secondary outcomes.

5.2 **Objectives**

The primary research hypothesis is that participants treated with n-3 PUFA will have greater improvement in asthma control as measured by the ACQ-6 test at 24 weeks post-randomisation versus participants treated with placebo.

The secondary research hypotheses are that participants treated with n-3 PUFA will:

- Have better asthma control as measured by the ACQ-7 test.
- Have better asthma related quality of life as measured by the asthma quality of life questionnaire (AQLQ).
- Have better health related quality of life measured by the euro-qol (5L-EQ-5D).
- Have better airway calibre as measured by peak expiratory flow (PEF), forced expiratory volume in 1 second (FEV₁) and forced expiratory flow at 50% of vital capacity (FEF₅₀).
- Have better peak nasal inspiratory flow (PNIF).
- Show n-3 PUFA is well tolerated with an acceptable safety profile.

Mechanistic research hypotheses are that the participants treated with n-3 PUFA will:

- Have reduced type 2 airway inflammation as assessed by FeNO, blood eosinophils and sputum eosinophils (subgroup).
- Have reduced urinary leukotriene E4 (uLTE4) and urinary prostaglandin D2 (PGD₂) concentration.
- Have improved Red Blood Cell (RBC) fatty acid concentration.
- Have increased sputum SPMs (subgroup).

Exploratory research hypotheses are:

- that participants treated with n-3 PUFA will have a reduced frequency of asthma attacks.
- those with higher baseline uLTE4 will have a greater response to n-3 PUFA.
- the greatest benefits will be evident in those with low baseline RBC omega-3 index.
- changes in RBC fatty acid concentration will relate to the clinical and mechanistic responses.

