6.4.5 Concomitant Care Standard Care

Patients will be managed according to the BTS/SIGN158 British guideline on the management of asthma (https://www.brit-thoracic.org.uk/quality-improvement/guidelines/asthma). This includes the use of bronchodilators, inhaled corticosteroids and theophylline. Participants may receive leukotriene receptor antagonists but not biologics. Acute asthma attacks may be managed with oral corticosteroids and antibiotics as appropriate. Patients will be withdrawn from the study if they undergo nasal polypectomy.

Concomitant medication

Patients must be receiving stable treatment for asthma and nasal disease related to N-ERD for at least 4 weeks prior to randomisation and not have any planned amendments for at least 4 weeks post-randomisation.

All concomitant medication including over the counter and herbal remedies will be recorded at baseline with any changes during participation recorded.

Non-permitted medication

The following medications are not permitted due to interactions, described in the SPC, with n-3 PUFA as outlined below and thus patients are **excluded** from the study (see section 6.3.1.3):

None

Omega-3 ethyl ester 90 should be used with caution in patients with known sensitivity or allergy to fish.

Increased monitoring

Concomitant medication requiring increased monitoring:

• Warfarin – monitored for increase in international normalised ratio (INR) and prothrombin time.

Omega-3 ethyl ester 90 as Omacor has been given in conjunction with warfarin without haemorrhagic complications. However, the prothrombin time must be checked when Omega-3 ethyl ester 90 is combined with warfarin or when treatment with Omega-3 ethyl ester 90 is stopped.

Sites are responsible for providing increased monitoring for participants receiving the abovementioned medication(s) and for any others the PI or sub-investigator deem appropriate. Results of additional monitoring procedures do not need to be recorded on the eCRF.

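### The standard-care substitution clause covers ACQ-6, so a score from a clinic attendance made for any reason within 4 weeks of week 24 may stand as the primary-outcome value

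*Protocol*

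**What the plan says.** The primary outcome is defined in Protocol section 6.5.1: "The primary outcome will be asthma control as assessed by change in asthma control questionnaire (ACQ)-6 mean score", assessed at 24 weeks after randomisation. The same section gives the recall period: "Patients are asked to recall how their asthma has been during the previous week".

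Section 6.6.1.9 opens the 24-week visit with ACQ-6 at the head of the list: "The following assessments should be completed 24 weeks post-randomisation: ACQ-6, PEF, PNIF, AQLQ, SNOT-22", followed by the clinic and laboratory measures. It then states that where any assessment on the list is "completed as part of standard care and within the time frame permitted by and requirements of this protocol, the results may be recorded" as the 24-week result. On timing it says "This visit may take place +/- 4 weeks of the scheduled date".

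The same permission appears for weeks 6, 12 and 18 in sections 6.6.1.6 to 6.6.1.8. The note under Figure 2 in section 6.6 repeats it, extends it to baseline within 28 days of randomisation, and gives the reason: "these observations can be recorded at the relevant time point to avoid patients having to repeat assessments unnecessarily".

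Two limits are stated: the visit window and compliance with the protocol's requirements. For ACQ-6, section 6.6.1.4 supplies one such requirement, that the form be completed on paper. Section 6.4.5 describes standard care and includes this: "Acute asthma attacks may be managed with oral corticosteroids and antibiotics as appropriate".

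**The concern.** The clause is sensible for spirometry, FeNO and blood tests, which need a clinic and are a burden to repeat. Applied to ACQ-6, it lets the primary endpoint be measured on a date set by the participant's clinical course and not by the trial calendar. The week-24 window runs from week 20 to week 28, and nothing separates a routine appointment from one sought because asthma had worsened. With one week's recall, a score from the second kind of attendance describes the week that prompted it.

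The endpoint would then mix scheduled scores with some event-driven ones. That adds variance. If substitution were also more frequent in one arm, the estimated difference would move. The protocol gives a reason why it might be: one exploratory hypothesis in section 5.2 is "that participants treated with n-3 PUFA will have a reduced frequency of asthma attacks".

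This is a rule about data collection, so the analysis plan cannot repair it afterwards. A scheduled form that was never completed cannot be recovered, and a substituted score that was never marked cannot be set aside.

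**Working it through.** **Does the clause reach the primary endpoint?** Four texts, read together:

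- Section 6.6.1.9 lists ACQ-6 among the 24-week assessments.
- The substitution sentence in that section applies to any assessment on the list.
- The Figure 2 note gives the purpose as sparing a repeat, so the standard-care value is meant to serve in place of the scheduled one.
- The stated limits concern the window and the protocol's requirements. The paper-form rule concerns format, not the reason for attendance.

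So a qualifying standard-care ACQ-6 may be entered as the primary-outcome value. The text permits this but does not require it.

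**The plan's own sample size (section 6.7).** Inputs: SD 0.67, difference 0.5, significance level 0.05 (two-sided assumed, since sidedness is not stated), power 90%, withdrawal 20%, 1:1 allocation.

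- Normal approximation: n = 2 × (1.960 + 1.282)² × 0.67² / 0.5² = 37.7, so 38 per arm; 38 / 0.8 = 47.5, so 48 per arm and 96 in total.
- Two-sample t-test (noncentral t): 39 per arm, power 90.2%; 39 / 0.8 = 48.75, so 49 per arm and 98 in total.

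The stated 98 is reproduced exactly by the t-test. The point challenges no stated figure, and the fix leaves 98 unchanged.

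**Illustration of size.** The protocol gives neither the share of scores that would be substituted nor how they would differ from scheduled ones. Both are assumptions here. Let a fraction q of participants have a substituted week-24 score that is D points worse than their scheduled score would have been, independently of that score.

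With q equal in both arms, the difference stays at 0.5 and the variance becomes 0.67² + q(1 − q)D². With 39 evaluable per arm (t-test):

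| q | D | Variance | SD | Power |
|---|---|---|---|---|
| 0 | – | 0.4489 | 0.670 | 90.2% |
| 5% | 0.5 | 0.4489 + 0.0119 = 0.4608 | 0.679 | 89.5% |
| 10% | 0.5 | 0.4489 + 0.0225 = 0.4714 | 0.687 | 88.8% |
| 10% | 1.0 | 0.4489 + 0.0900 = 0.5389 | 0.734 | 84.4% |
| 20% | 1.0 | 0.4489 + 0.1600 = 0.6089 | 0.780 | 79.8% |

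With unequal q, the estimated difference moves by (q on placebo − q on active) × D:

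- 10% against 5%, D = 1.0: 0.05 × 1.0 = 0.05 points, or 10% of the 0.5 target.
- 15% against 5%, D = 1.0: 0.10 × 1.0 = 0.10 points, or 20% of the target.

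With equal q the shift is zero. If substituted scores were better than scheduled ones, D would be negative. The variance term, which uses D², would be the same and any shift would change sign.

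**The case against.** The strongest reply is that the harmful mechanism is inferred. No section says that ACQ-6 is administered at attendances prompted by worsening. Section 6.4.5 says how attacks may be treated and does not mention the questionnaire. The standard-care attendance that the protocol does describe, in section 6.8.1, is a routine appointment. The week-24 visit also requires trial-specific items, such as the capsule count, the food frequency questionnaire and the research urine sample. It will usually take place in any case, with the trial form to hand. All of this stands, and it is why the size cannot be stated and may be negligible.

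Several stronger readings are tempting and are not supported:

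- A reader might infer that any ACQ-6 score qualifies. It must fall in the window and meet the protocol's requirements, including the paper form.
- A reader might infer from the permissive wording that staff choose after seeing the score. The protocol describes no such selection, and section 6.9.2 keeps participants, care providers and outcome assessors blind, so a choice could not follow known allocation.
- A reader might infer that a substituted score could come before the trial treatment has had time to act. The earliest week-24 value is at week 20.
- A reader might infer that substituted scores are always worse. One taken after an attack had been treated could be better.

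It can also be said that the choice between several values in one window, and sensitivity analyses by source, belong in the SAP. That is right, and their absence from the protocol is not the complaint. What remains is the collection rule itself, which the protocol states and which includes the primary outcome.

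**Conclusion.** The point holds in a limited form. As written, a qualifying standard-care ACQ-6 within 4 weeks of week 24 may replace the scheduled score as the primary-outcome value, whatever led to the attendance. If some of those attendances were prompted by symptoms, the timing of the primary endpoint would depend on the outcome.

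The consequence is added variance. The estimate shifts only if substitution differs between arms. At an assumed 10% substitution with scores 0.5 to 1.0 points worse in both arms, power falls from 90% to between 89% and 84%; at 20% and 1.0 point it is 80%. These figures rest entirely on assumed rates, and the true effect may be close to nil.

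A reader might go further and conclude that the trial risks a false positive finding. The documents do not support that. Under the blind, and with no treatment effect, substitution should be equally frequent in both arms, so type I error is not inflated. Priority is low to moderate. The case for acting is that the change costs little and cannot be made after the data are collected.

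**What to change.** Exempt ACQ-6 from the substitution clause, at least in section 6.6.1.9 and preferably also in sections 6.6.1.6 to 6.6.1.8 and the Figure 2 note. Wording to this effect would do: *This provision does not apply to ACQ-6. The trial ACQ-6 is completed for the scheduled time point whether or not one was done in standard care, and it takes precedence as the study value.* Keep the substitution for tests that need a clinic.

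If a standard-care ACQ-6 is the only week-24 value, record it with a source flag. Keeping it in the primary analysis avoids adding missing data. Repeating that analysis without flagged values shows whether it matters.

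The cost is a short protocol amendment, touching up to five places and following the approval route in section 7.4, and one eCRF field. A few participants would answer six questions twice, on a form that can be completed at home. The sample size does not change.
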